1.0 Study Summary

Study Title	Neonatal Esophagus and Airway Interactions in Health and Disease: Mechanisms and Management of Infant Dysphagia
Study Design	Single arm observational study
Primary Objective	Our overall aims are to identify novel diagnostic aerodigestive targets, define effective therapeutic interventions, and advance the mechanistic basis of therapeutic outcomes-i.e., full oral feedings.
Secondary Objective(s)	
 1) Examine the differences in outcomes among preterm born vs. full term born 2) Examine the differences in outcomes among those with normal versus abnormal VFSS
Research Intervention(s)/Investigational Agent(s)	Providing esophageal manometry concurrent with video fluoroscopy swallow study (VFSS) in order to determine sensory-motor dysphagic mechanisms which will better inform treatment options
IND/IDE #	N/A

PROTOCOL TITLE: Neonatal Esophagus and Airway Interactions in Health and Disease: Mechanisms and Management of Infant Dysphagia

Study Population	
All infants will have a diagnostic VFSS scheduled.
 
Inclusions: Infants with feeding-related aerodigestive symptoms who are \leq 60 weeks PMA (both pre-term and full-term) who are orally feeding $\geq 25\%$ of at least 50% of their feeds who are on full enteral feeds with no more than 1LPM NC respiratory support.
 
Exclusions: Genetic or metabolic syndromes, IVH grade III or greater, moderate to severe HIE, craniofacial, airway or foregut malformations or ENT or neuro surgeries. Infants who are exclusively breastfeeding are also excluded.

Sample Size	60
Study Duration for individual participants	Up to 4 weeks (initial manometry study with diagnostic VFSS, repeat manometry at 4-6 weeks as relevant), will follow feeding outcomes and growth and developmental outcomes for 1 year
Study Specific Abbreviations/ Definitions	
VFSS video-fluoroscopy swallow study
 
LP laryngeal penetration
 
LA laryngeal aspiration

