2.0 Objectives

2.1 Purpose, Specific Aims or Objectives

- Our overall aims are to identify novel diagnostic aerodigestive targets, define effective therapeutic interventions, and advance the mechanistic basis of therapeutic outcomes. Infants with aerodigestive and feeding difficulties, who had VFSS undergo Manometry study to ascertain the mechanisms of normal or abnormal swallowing. Parent-preferred therapy is implemented. Changes in therapy modes are documented. Repeat manometry study is undertaken at time-2, which is 2-4 weeks after the initial study where feasible (this may happen in those with oral feeding failures).
- Based on the VFSS results evaluations, there are 2 possible scenarios: those with abnormal or normal results. Parent preferred therapeutic feeding (flow change, thickener change, no change) strategy is implemented and we will simply monitor the progress of the feeding efficiency till discharge or four weeks, whichever is earlier. There are 2 possible outcomes: feeding success, i.e., full oral feeds without symptom requiring intervention or feeding failure, i.e., those needing any tube feeding.
- We will review the motility characteristics of the successful and failure cases to identify the diagnostic markers.

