2.2 Hypothesis

- The central unifying hypothesis supported by our preliminary data is that VFSS with the addition of Manometry along with parent preferred feeding strategy is more effective in preventing long term feeding tubes in infants with aerodigestive problems and feeding difficulties.
- **Primary Hypothesis:** The addition of manometry for diagnostics and parent preferred therapy for management is more effective than VFSS with provider recommendations alone for achieving primary outcome.
- **Secondary Hypotheses:** 1) The sensory- motor characteristics of pharyngo-esophageal motility markers are distinctive between normal and abnormal VFSS results. 2) Clinical outcomes are distinct with flow modification and thickener use.

3.0 .Background

3.1 Relevant prior experience and gaps in current knowledge.

- Dysphagia or abnormalities of swallowing, is a heterogeneous condition of multiple etiologies. Pharyngeal phase is the most critical phase since imprecise regulation is associated with airway consequences such as laryngeal penetration and airway aspiration. Exact prevalence is not known, but is estimated to be about 30% to 60% among neonatal ICU graduates. Although these numbers highlight the economic burden, they ignore the quality of life for both patients and parents. The lack of a pathophysiology guided diagnostic and safe feeding management strategies continue to be critical barriers to progress in this field. The current proposal focuses on the dynamic changes in the integrative physiology of the neonatal pharynx, upper esophageal sphincter (UES), lower esophageal sphincter (LES) and esophagus during swallowing and GERD; all of which are potential therapeutic targets for neonates with dysphagia. Current treatment approaches in dysphagic infants are likely to fail due to unclear therapeutic targets. Such high risk infants also suffer chronic morbidity, longer hospitalizations, re-admissions, and account for an unacceptable health care burden. Designing effective symptom-based management is very difficult.

3.2 Relevant preliminary data.

PROTOCOL TITLE: Neonatal Esophagus and Airway Interactions in Health and Disease: Mechanisms and Management of Infant Dysphagia

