6.0 Procedures Involved*

6.1 Study Design

- Study design and setting: Eligible subjects (study) will undergo diagnostic VFSS in combination with manometry, either concurrent or sequential. They will have parental choice of preferred feeding therapy. The data is from single center prospective observational study. The controls are those who had VFSS alone with provider recommendations from the same single center.
- Patient population and characteristics: (i) Study and control infants have oral feeding difficulties with symptoms requiring interventions/monitoring. (ii) They have diagnostic need for VFSS due to aerodigestive and feeding difficulties. (iii) Study subjects must have a signed informed consent from parent/legal guardian prior to manometry study. Control subjects did not require consent as they were historical controls.
- Inclusion criteria: Infants with feeding-related aerodigestive symptoms who are \leq 60 wks PMA (both pre-term and full-term) who are orally feeding \geq 25% of at least 50% of their feeds who are on full enteral feeds with no more than 1LPM NC respiratory support. All infants will have a diagnostic VFSS scheduled.
- Exclusion criteria: Genetic or metabolic syndromes, grade III or greater, moderate to severe HIE, craniofacial, airway or foregut malformations or ENT or neuro surgeries. Infants who are exclusively breastfeeding are also excluded.
- Test-1: VFSS with concurrent or sequential pharyngo-esophageal manometry along with standard safety metrics. Esophageal and pharyngeal provocation induced

PROTOCOL TITLE: Neonatal Esophagus and Airway Interactions in Health and Disease: Mechanisms and Management of Infant Dysphagia

aerodigestive reflexes will be tested. Oral feeding challenge test is performed during manometry. The same procedures without VFSS will be repeated at Time-2 where feasible and relevant.

- Overall Study Endpoints: Primary endpoint is therapeutic success defined as full oral feeding without symptoms requiring intervention at 4 weeks (for outpatient studies and those still admitted at 4 weeks) or discharge, whichever is earlier. Secondary clinical end points include growth velocity and feeding outcomes at 1 year.
- Methods to overcome Potential Confounders: It is NICU standard to document in EPIC: i) Daily documentation of symptoms, medication use, feeding methods and duration, feeding volume and weight, ii) Weekly documentation of growth velocity (weight, length, head circumference).

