7.0 Sharing of Results with Subjects*

- 7.1 Manometry results are shared with the parents at the time of the study. Parents decide on their preferred feeding approach (flow change, thickener change, no change) and if the patient is inpatient, this is shared with the medical team.

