16.0 Data Management* and Confidentiality

16.1 Data Analysis Plan

- Descriptive statistics will be reported as median (IQR), mean \pm SD or total number and percentage for demographics and clinical characteristics. For PPG vs FOD historical control comparisons, two-sample t-test or ANOVA will be used for the continuous variables and chi-squared or Fischer's exact tests will be used for the categorical variables, whichever is appropriate. Non-parametric method (e.g. Wilcoxon) might be used if the data is not normally distributed. Normality will be assessed using Shapiro-Wilks test and visually inspection of the data. For other Normal vs Abnormal VFSS and the effect of parent preferred therapy -flow modification or thickener use) comparisons, due to the nature of the repeated measure of the data, repeated measure ANOVA for continues measured variables and Generalized estimating equation (GEE) for categorical variables, to predict the likelihood of the specific response, will be used as to make the between group comparisons. Compound symmetry (CS) will be specified for the covariance structure of the repeated data. Bonferroni correction will be used to conserve the overall type I error at $\alpha=0.05$. To characterize the association between the disease comorbidities and feeding success, simple and multiple logistic regression analysis will be performed. Statistical Analysis Software, version 9.4 (SAS Institute Inc., Cary, NC, USA)

- 16.2 Data will be stored in RedCap and each subject will have a file which is kept in a secured locked location.

- 16.3 Data will be verified by at least two individuals on the study team

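### The flow-versus-thickener comparison in 16.1 states no confounder adjustment, although parents choose therapy after manometry results are shared and after VFSS evaluation

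*Combined protocol and SAP*

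**What the plan says.** Secondary hypothesis 2 in section 2.2 reads: "Clinical outcomes are distinct with flow modification and thickener use". Section 16.1 serves it with comparisons described as "the effect of parent preferred therapy -flow modification or thickener use) comparisons". Repeated-measures ANOVA is assigned to continuous outcomes and GEE to categorical ones, with compound symmetry and a Bonferroni correction. No covariate, stratification, matching or propensity method is named.

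Therapy is not randomised. Section 7.1 says "Manometry results are shared with the parents at the time of the study" and continues: "Parents decide on their preferred feeding approach (flow change, thickener change, no change". Section 2.1 puts the choice after the swallow study: "Based on the VFSS results evaluations, there are 2 possible scenarios: those with abnormal or normal results". On later switching, 2.1 says only "Changes in therapy modes are documented".

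Section 6.1 has an item that opens "Methods to overcome Potential Confounders: It is NICU standard to document in EPIC" and then lists what is charted (symptoms, medication, feeding, growth). The only multivariable model in 16.1 is a logistic regression of feeding success on comorbidities. Section 1.0 calls the design a "Single arm observational study".

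**The concern.** Parents who have been told the manometry findings, and who probably know the VFSS result (implied by 2.1, not stated), may lean towards one therapy when the findings look worse. The protocol also expects such findings to bear on outcome: 2.1 plans to review motility in successes and failures to find diagnostic markers. Both links needed for confounding by indication are therefore present in the design.

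At stake is how a flow-versus-thickener difference would be read. Defining effective interventions is among the overall aims, and 16.1 uses the word effect. An unadjusted difference could be taken as evidence for one therapy when it partly reflects case mix.

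**Working it through.** **1. Is adjustment provided anywhere?**

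| Provision | What it covers | Confounding of the therapy comparison? |
|---|---|---|
| 16.1, ANOVA/GEE | Between-group comparison of repeated data | No covariates listed |
| 16.1, compound symmetry | Correlation within an infant | No |
| 16.1, Bonferroni | Multiplicity | No |
| 16.1, logistic regression | Comorbidities and feeding success | Therapy not named |
| 6.1, confounder item | Routine charting | Data collection only |

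The VFSS comparison and the therapy comparison share one sentence in 16.1. If both factors were meant to enter one model, 16.1 does not say so.

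**2. Are the groups defined?** Section 7.1 offers three options: flow change, thickener change, no change. Section 16.1 compares two states: flow modification and thickener use. These are not the same variable. An infant already on thickener whose parents choose no change is still a thickener user. No section places that infant, an infant who switches, or one who receives both.

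**3. The plan's own figure.** No power or sample size is given for this comparison. The 90% in 3.3 belongs to the primary comparison. It is reproduced by a one-sample test of 80% against a fixed 60% with n = 60: 92.3% exact (44 or more successes, upper tail 0.0221), or 90.5% by the continuity-corrected normal approximation. This point does not affect it.

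**4. Illustration of size. All inputs are assumed.** There is no therapy effect; success is 80% with a normal and 60% with an abnormal VFSS; the test is a two-sided pooled chi-squared test of feeding success; the level is 0.05/2 = 0.025 (two comparisons; 16.1 does not give the number).

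Success in a group = (share abnormal × 0.60) + (share normal × 0.80).

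- Abnormal VFSS 80% vs 40%: 0.8×0.6 + 0.2×0.8 = 0.64; 0.4×0.6 + 0.6×0.8 = 0.72. Spurious difference: 8 points.
- Abnormal VFSS 70% vs 50%: 0.7×0.6 + 0.3×0.8 = 0.66; 0.5×0.6 + 0.5×0.8 = 0.70. Spurious difference: 4 points.
- Balanced at 60%: 0.6×0.6 + 0.4×0.8 = 0.68 in both.

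Rejection rates by exact binomial enumeration:

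| Abnormal VFSS | 30 vs 30 | 20 vs 20 |
|---|---|---|
| 80% vs 40% | 6.0% | 4.7% |
| 70% vs 50% | 3.4% | 3.0% |
| Balanced | 2.6% | 2.5% |

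The 30 vs 30 column assumes no infant has no change; 20 vs 20 assumes a third do.

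**5. Can an adjusted binary model be supported?** With 60 infants and the 60% and 80% success rates in 3.3, failures number 60×0.40 = 24 or 60×0.20 = 12. A three-level therapy factor (2 parameters), VFSS result (1) and oral intake (1) make 4 parameters, so 12/4 = 3.0 to 24/4 = 6.0 failures per parameter. One manometry finding makes 5, giving 2.4 to 4.8.

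**The case against.** The strongest reply is that this is an unpowered secondary comparison in a study that calls itself observational, resting on one loose word. Hypothesis 2 says only that outcomes differ, so the plan does not commit the authors to a causal claim. That is fair and keeps the point minor. It does not supply the missing adjustment.

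The illustration can also be challenged, and much of that stands. It models a chi-squared test that 16.1 does not assign to this comparison, and it says nothing about manometry-response outcomes. A reader might take 6.0% as the trial's error rate. The documents do not support this: it comes from a strong assumed imbalance, and the milder case gives 3.4%.

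Three other stronger readings should be set aside:

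- A reader might infer that 16.1 adjusts for nothing. Bonferroni is stated; what is missing is covariate or confounder adjustment.
- A reader might infer that the outcome is a manometry response recorded at Test-1, before the choice, and so could not be affected by it. Hypothesis 2 concerns clinical outcomes, and 16.1 does not say that a Test-1 response is the outcome here.
- A reader might infer that grouping by first choice settles the grouping question. It does not, because first choice does not map onto thickener use.

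Finally, covariate adjustment is weak where failures are few. That stands, and it is why the fix includes a descriptive label.

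**Conclusion.** The concern holds as a minor point. Section 16.1 compares parent-chosen therapies as an effect, with no stated covariate or confounder adjustment, while 7.1 and 2.1 let the choice follow findings that may predict outcome. The documents show that confounding by indication is possible; its size and direction cannot be derived from them. On the assumed inputs with 30 versus 30 infants, the false-positive rate is 3.4% to 6.0% against 2.6% with balance.

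The missing group definition matters as part of the same comparison; alone it would be only missing detail. A reader might extend the point to the main result, but the primary comparison is with historical controls and does not divide infants by therapy.

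**What to change.** In 16.1:

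1. Add VFSS result and baseline oral intake as covariates in the therapy ANOVA and GEE, and show adjusted beside unadjusted results.
2. Replace effect with association, and state that confounding by manometry findings remains.
3. For sparse binary outcomes such as feeding success, label the comparison descriptive if the adjusted model cannot be supported.
4. Define the analysis groups so that the three options in 7.1 and the two groups in 16.1 are reconciled, including no change, combined and switched therapy.

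The cost is wording and one extra model per outcome. No infants are added: every infant has a VFSS, and oral intake is already an eligibility criterion. Some precision is lost and residual confounding can remain. This version is dated 10/2/20 and planned enrolment ended 7/20, so the adjustment must be labelled post hoc if outcomes had already been seen when it was added.

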- Three references are attached below in this section that lend support to our investigations, difficulties with strict protocols and need for personalization and parent preferred pragmatic therapies. Complimentary protocols (feeding outcomes in dysphagia, mechanisms of dysphagia, outcomes in gastrostomy bound infants) will address the original study aims as well. Updated statistical procedures based on the advice of our statistician, [name], PhD, DSMB team, and our Program Project Group is shown below.

3.3 Updated statistical procedures:

- The design of the Patient Preferred Trial has been modified to a single arm observational study with patients who have not achieved PO at the time of study or PO with feeding difficulties, comparing VFSS and manometry vs VFSS only (the historical control) on feeding outcomes. The primary outcome is success rate at discharge. We will prospectively follow 60 infants who are not fully PO or PO and symptomatic at the time of study. Based on our Feeding Outcomes of Dysphagia Study (vs. historical control), the success rate at discharge is around 60%. With 60 patients enrolled, we will have 90% power to detect an absolute increase of 20% from 60% for those who do not have treatment informed by manometry (historical control) to 80% in those in the manometry informed group with two-sided type I error of 0.05. Achievement will be assessed by tracking feeding methods at discharge or 4 weeks whichever is earlier and then at 1 year.
- [name], Peng J, Moore R, Saavedra J, Shepherd E, Fernandez S, Erdman SH, DiLorenzo C. Impact of personalized feeding program in 100 NICU infants: pathophysiology-based approach for better outcomes. *J Pediatr Gastroenterol Nutr.* 2012 Jan;54(1):62-70.
- [name], Stoner E, Gupta A, Bates DG, Fernandez S, Di Lorenzo C, Linscheid T. Evaluation and management of neonatal dysphagia: impact of pharyngoesophageal motility studies and multidisciplinary feeding strategy. *J Pediatr Gastroenterol Nutr.* 2009 Feb;48(2):186-92
- [name], Khot T, Moore R, Malkar M, Gulati IK, Slaughter JL. Feeding Methods at Discharge Predict Long-Term Feeding and Neurodevelopmental Outcomes in Preterm Infants Referred for Gastrostomy Evaluation. *J Pediatr.* 2017 Feb;181:125-130

3.4 Scientific or scholarly background for, rationale for, and significance of the research based on the existing literature and how will it add to existing knowledge

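### With about 12 to 24 feeding failures among 60 infants, the comorbidity logistic models in 16.1 should be fitted by Firth's penalised likelihood rather than ordinary maximum likelihood

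*Combined protocol and SAP*

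**What the plan says.** Section 16.1 (Data Analysis Plan) states, for the link between comorbidities and feeding success, that "simple and multiple logistic regression analysis will be performed", using SAS 9.4. It lists no comorbidities, sets no limit on their number, names no penalised or exact method, and does not say whether historical controls enter the model.

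The size of the data set comes from section 3.3 (Updated statistical procedures): "We will prospectively follow 60 infants who are not fully PO or PO and symptomatic at the time of study". There the control rate is given by "the success rate at discharge is around 60" per cent, and the target is "80% in those in the manometry informed group".

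A separate analysis rests on the same failures. Section 2.1 says: "We will review the motility characteristics of the successful and failure cases to identify the diagnostic markers". No test or list of measures is given for it. Section 16.1 does name a Bonferroni correction at an overall 0.05. It comes after the VFSS-result and feeding-therapy comparisons and before the logistic regression, and its family of tests is not defined.

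**The concern.** In logistic regression the rarer outcome limits what can be estimated, and here that is failure. If a comorbidity is absent from every failure, or the comorbidities together divide the outcomes perfectly, the maximum-likelihood odds ratio is infinite and its Wald interval is useless. Short of that, small-sample bias pushes finite odds ratios away from 1. A plan that succeeds on its primary endpoint leaves fewer failures and makes both problems worse. At stake is which comorbidities are reported as linked to feeding failure, and how strongly.

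The motility review shares the shortage of failures, but its gap is different: the document does not show which multiplicity rule applies to it.

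**Working it through.** **1. The plan's own figure.** Section 3.3 claims 90% power for 60% against 80% with 60 infants and "two-sided type I error of 0.05". As a one-sample test against a fixed 60%:
- √60 × 0.20 = 1.549; 1.96 × √(0.6 × 0.4) = 0.960; √(0.8 × 0.2) = 0.4.
- Without continuity correction: (1.549 − 0.960)/0.4 = 1.47, power 0.930.
- With the correction 0.5/√60 = 0.065: (1.549 − 0.960 − 0.065)/0.4 = 1.31, power 0.905.

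The 90% is reproduced, so 60 infants, 60% and 80% are the right inputs.

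**2. Expected failures**, 60 × (1 − success rate):
- 80% success: 12 (90% binomial range 7 to 17).
- 60% success: 24 (18 to 30).

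**3. Failures per covariate**

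| Covariates | 12 failures | 24 failures |
|---|---|---|
| 3 | 4.0 | 8.0 |
| 5 | 2.4 | 4.8 |
| 8 | 1.5 | 3.0 |

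**4. Infinite estimates, by hand.** Take a comorbidity of prevalence π that is unrelated to outcome. The chance that no failure has it is (1 − π)^f for f failures. For k independent comorbidities, the chance that at least one has such an empty cell is 1 − [1 − (1 − π)^f]^k.

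| f, π | One comorbidity | k = 3 | k = 5 | k = 8 |
|---|---|---|---|---|
| 12, 20% | 0.8^12 = 6.9% | 19% | 30% | 43% |
| 12, 30% | 0.7^12 = 1.4% | 4% | 7% | 11% |
| 24, 20% | 0.8^24 = 0.5% | 1.4% | 2.3% | 3.7% |

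This holds the failure count fixed and ignores separation by combinations of covariates, so it understates the risk.

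**5. Infinite estimates, by simulation** (60 infants, independent binary comorbidities; number, prevalence and effect are assumptions).
- No true effect, 80% success, with 1/3/5/8 covariates: 9/24/35/47% of fits at 20% prevalence and 2/8/11/15% at 30%.
- Prevalences of 15-40%, one true odds ratio of 3, 80% success: about 10-17% with 3 covariates, 17-24% with 5 and 28-36% with 8, across repeated simulations.
- The same setting at 60% success: about 1-5%.
- A favourable case at 80% success, every comorbidity with 30% prevalence and a true odds ratio of 2: 1.7/3.0/7.4% with 3/5/8.

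**6. Bias in the finite fits** (geometric mean odds ratio, 3/5/8 covariates).
- True odds ratio 3, 80% success: 3.2/3.6/4.0.
- True odds ratio 2, 60% success, 20% prevalence: 2.13/2.18/2.35. Having 24 failures removes most separation but not the bias.

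**7. Error rate.** With no true effect and 80% success, a single Wald test rejected 3-5% of the time.

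**8. Firth's method.** In the setting of step 6 with a true odds ratio of 3, estimates were always finite and averaged 2.9 to 3.05. With 5 covariates, on the finite fits, the root mean squared error of the log odds ratio was about 0.74, against 0.92 for maximum likelihood.

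**The case against.** The best defence is that the count of 12 is conditional and the covariates are unstated. Section 16.1 does not confine the model to the study infants, and section 6.1 describes same-centre controls. If, say, 60 controls with 60% success were pooled (an assumption; their number is not given), expected failures would be 12 + 24 = 36, and separation fell below 1% of fits with 3 to 8 covariates. Simple models with common comorbidities are also largely safe: about 2% at 30% prevalence. All this stands and limits the point to several comorbidities modelled in the study infants alone. It does not remove it, because nothing in 16.1 rules that case out.

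Stronger readings are tempting and should be resisted:
- A reader might infer that the regression is bound to fail. Most fits in the 15-40% prevalence setting are finite even with 8 covariates.
- A reader might infer false-positive comorbidity tests. Step 7 shows that single tests hold their level; the harm is unstable and inflated estimates.
- A reader might infer poor prediction in new infants. Section 16.1 sets out to describe association and plans no prediction use of this model.
- A reader might infer that the marker search has no multiplicity control, and compute a large familywise error for a grid of reflex measures by stimuli. The plan states no such grid and does name Bonferroni. What can be said is that the correction's reach is undefined and is not tied to the review in section 2.1.

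**Conclusion.** The point holds as a modest, avoidable weakness of a secondary analysis. With several binary comorbidities in the 60 study infants, ordinary logistic regression can give an infinite odds ratio in roughly 10-35% of fits at the design target and 1-5% at 60% success, with finite odds ratios biased away from 1 in both cases. These figures rest on 3 to 8 independent comorbidities with 15-40% prevalence, one true odds ratio of 3, and no pooling of controls. Across the other settings tried at 80% success, the figure ran from about 2% to 47%. The comparison of success with the historical control rate is untouched.

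For the motility markers the conclusion is narrower: a clarification of which tests the existing correction covers.

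**What to change.** In section 16.1, state that the simple and multiple logistic models for feeding success will be fitted by Firth penalised likelihood (PROC LOGISTIC, FIRTH option), with profile-likelihood confidence limits in place of Wald limits. This is an option in the software already named and needs no further infants or data. The price is slight shrinkage of the odds ratios. If controls are pooled, the separation risk it guards against is already small.

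In the same section, add that the Bonferroni correction also covers the success-versus-failure motility comparisons of section 2.1, define that family of tests, and report the results as candidate markers. The cost is one or two sentences and probably fewer markers declared.
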